**5.2 Selection of study instruments**

**Baseline questionnaire:** During the baseline questionnaire, we will obtain demographic data including age, gender, race, ethnicity, religion, relationship status, relationship of the caregiver to the patient, education level, and annual household income [Appendix A].

**Qualitative interview guide:** We will use a semi-structured interview guide that will explore 1) caregiver perception of the acceptability and content of the intervention; and 2) caregiver perceptions of the benefits of receiving the intervention. Facilitators will use probes to obtain comprehensive understanding of the caregivers’ perspectives. The semi-structured interview guide is detailed in Appendix B. The interview will last approximately 30 minutes. The participants will not be required to complete any additional study instruments. The qualitative interview will be conducted in-person or over the telephone (Appendix C).

**Training of research coordinator to conduct qualitative interviews:** We will utilize the MGH Cancer Outcomes Research Group (CORE) extensive experience training research assistants to conduct semi-structured qualitative interviews with the use of the interview guide. The research assistant will first complete an initial training with [name], a psychologist with extensive experience conducting qualitative interviews. They will then conduct mock practice interviews with the presence of both [name] (PI) as well as [name] (co-investigator). They will be provided direct feedback regarding their qualitative interview technique. Lastly, the research assistant will be supervised by [name], [name] (a psychologist and co-investigator) or [name] during their first two qualitative interviews with

Psychological Intervention to Promote Coping for Caregivers of Patients Undergoing Hematopoietic Stem Cell Transplantation (HCT)  
Protocol version 1/ 10-3-2016

study participants to ensure appropriate interview techniques. Of note, the research assistant will utilize a semi-structured interview guide (Appendix C) for all interviews.

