## **5.2 REGISTRATION PROCEDURES**

### **5.2.1 Registration process for DF/HCC and DF/PCC Institutions Registrations**

After completion of baseline questionnaires, caregivers will be registered centrally with the DF/HCC Office of Data Quality (ODQ) central registration system. Registration Process for DF/HCC Institutions DF/HCC Standard Operation Procedures for Human Subject Research Titled Subject Protocol Registration (SOP# REGIST-101) must be followed. For each study participant, we will complete the following registration procedures:

- We will obtain written informed consent from the participant prior to the performance of any protocol specific procedures or assessments.
- We will complete the ODQ protocol-specific eligibility checklist using the eligibility assessment documented in the research chart. Only eligible participants will be registered. To be eligible for registration to the protocol, the participant must meet all including and exclusion criterion as described in this protocol and reflected on our eligibility checklist.
- We will fax the eligibility checklist(s) and all pages of the consent form(s) to the ODQ at [contact].
- The ODQ Registrar will a) review the eligibility checklist, b) register the participant on the protocol, and c) randomize the participant when applicable.
- An email confirmation of the registration will be sent to the Overall PI, study coordinator(s), treating investigator, and registering person immediately following the registration.

We are requesting a a HIPAA Waiver of Alteration to Use or Disclose of Protected Health Information from the IRB. This waiver is being requested to identify potential participants from a minimal chart review.

Psychological Intervention to Promote Coping for Caregivers of Patients Undergoing Hematopoietic Stem Cell Transplantation (HCT)  
 Protocol version 1/ 10-3-2016

In accordance with the DF/HCC policy, this Waiver: (1) is being sought solely to review Protected Health Information as necessary to prepare a research protocol, (2) will not include removing Protected Health Information from the Covered Entity by the researcher, and (3) the Protected Health Information for which we are requesting access is necessary for the research purposes.

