### **5.5 Description of Study Process**

#### **5.5.1 Study Instrument Administration**

After signing consent, we will schedule caregivers for their intervention visits with [name]. Upon completion of the intervention visits around day +90 (+/- 15 days) post-HCT, the trained research assistant or the principal investigator will conduct the qualitative exit interviews with study participants using a semi-structured interview guide (Appendix B). The interview will last approximately 30 minutes. Participants will be asked to be frank and will be reminded that there is no right or wrong answer to any question. Participants will also be reminded that they may refuse to answer any question that they choose. Drs. [name] (Principal investigator), and [name] (clinical psychologist and co-investigator) will be available to provide support and supervise the qualitative interview process.

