## **6 Ethical and Legal Issues**

### **6.1 Confidentiality**

All patient information will remain confidential and stored on Partners computers. Identifiers such as name will only be used during the initial data retrieval process and can be destroyed once all data records have been obtained and data analysis completed.

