#### **7.3 Analysis Plan:**

**Phase 1 Data Analysis and Interpretation:** We will use descriptive statistics to summarize the demographic and clinical characteristics of the caregivers enrolled in the study. Our planned sample size (n = 5-10) will allow us to collect comprehensive feedback about the intervention and ensure that we have sufficient number of participants to achieve thematic saturation. The qualitative component of the

Psychological Intervention to Promote Coping for Caregivers of Patients Undergoing Hematopoietic Stem Cell Transplantation (HCT)  
Protocol version 1/ 10-3-2016

exit interviews will 1) explore caregiver perception of the acceptability and content of the intervention; and 2) explore caregiver perceptions of the benefits of receiving the intervention. We will also evaluate the acceptability of the intervention by exit interview responses. We will analyze the qualitative data from the exit interview according to the NIH-Best Practices for Mixed Methods research in Health Sciences for applicability, preferences, clinical relevance, intervention length/timing, and challenges. Study staff will independently review the qualitative interview transcripts to create a thematic framework for interpretation. Two independent coders (Drs. [name] and [name]) will independently code the data to enhance validity and credibility, until high reliability is achieved (Kappa >0.080). Discrepancies will be resolved by comparison to raw data and reviews by Drs. [name], [name], [name], and [name].

We will utilize the qualitative data obtained from phase 1 and clinicians' experience to finalize the multicomponent psychological intervention. Specifically, we will refine the following aspects of the intervention:

- **Intervention content:** We will use caregivers' feedback to confirm the relevance of the intervention content, and to revise content as needed. For instance, if caregiver report that they would have liked to focus on more active coping strategies, we will increase the balance between change- and acceptance-oriented (e.g., mindfulness) approaches. To further enhance the intervention, we also may integrate caregivers' real-life concerns as examples throughout the protocol when introducing the use of coping skills and strategies.

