## 9 Appendices

### Appendix A: Baseline Questionnaire

#### Caregiver Demographics

Please check the appropriate box or boxes.

1. Date of birth (mm/dd/yyyy) \_\_\_\_\_
  
2. Gender
  - Man
  - Woman
  - Other
  
3. Relationship to patient
  - Married or living as if married
  - Non-cohabiting relationship
  - Divorced/Separate
  - Child (daughter or son)
  - Parent (mother or father)
  - Sibling (brother or sister)
  - Friend
  - Other family
  
4. Ethnicity
  - Hispanic or Latino
  - Not Hispanic or Latino
  
5. Race (please check all that apply)
  - American Indian or Alaskan native
  - Asian
  - African American or Black
  - Native Hawaiian or other Pacific Islander
  - White
  - Other (please specify) \_\_\_\_\_
  
6. Religion
  - Catholic Christian
  - Other Christian (such as Protestant, Orthodox, etc.)
  - Jewish
  - Muslim
  - Atheist
  - None
  - Other (please specify) \_\_\_\_\_

Psychological Intervention to Promote Coping for Caregivers of Patients Undergoing Hematopoietic Stem Cell Transplantation (HCT)  
Protocol version 1/ 10-3-2016

7. Please indicate your highest or current education level

- 11th grade or less
- High school graduate or GED
- 2 years of college/AA degree/Technical school training
- College graduate (BA or BS)
- Masters degree
- Doctorate/Medical degree/Law degree

8. Current employment status

(please check all that apply):

- Employed (full-time or part-time)
- Caring for home or family (not currently employed and not looking for paid work)
- Unemployed and looking for work
- Unable to work due to illness or disability
- Retired
- Student
- Other (please specify) \_\_\_\_\_

9. Please indicate how long you have known the patient: \_\_\_\_\_ years

10. Do you live in the same residence as the patient?

- Yes
- No

Your name: \_\_\_\_\_

Please enter your email address  
(will only be used if necessary):

\_\_\_\_\_

What is the best phone number to use if we needed to reach you?

\_\_\_\_\_

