15. Since going to the study visits, how often have you used any of the skills or strategies on your own?

- A. Daily
- B. Few times/ week
- C. Once or twice
- D. Never

Additional Comments:

16. Is there anything else that you found helpful about this program?

17. Is there anything else that you found *not* helpful about this program?

18. What other kinds of programs focusing on improving your well-being (if any) would have been helpful *prior* to your loved ones' stem cell transplantation?

Psychological Intervention to Promote Coping for Caregivers of Patients Undergoing Hematopoietic Stem Cell Transplantation (HCT)  
Protocol version 1/ 10-3-2016

19. What other kinds of programs focusing on improving your well-being (if any) would have been helpful *immediately after* your loved ones' stem cell transplantation?

20. What other kinds of programs focusing on improving your well-being (if any) would be helpful to you now?

21. People learn information in different ways. What would you prefer in terms of how the intervention is administered?

- A. One-on-one visit with a clinician
- B. Reading information from a pamphlet
- C. Watching an informational video
- D. Telephone contact with a clinician
- F. Getting information from a mobile app
- G. Video (skype-like) sessions
- H. Group-based sessions with other caregivers

Additional Comments:

22. Is there anything else that you would like to add that we have not discussed?

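### Does the mismatch between the baseline variables promised in section 5.2 and the Appendix A form call for a change to the plan?

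*Combined protocol and SAP*

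**What the plan says.** Section 5.2 (Selection of study instruments) describes the baseline questionnaire as collecting demographic data. It introduces the variables as an open list of nine that closes with "relationship status, relationship of the caregiver to the patient, education level, and annual household income [Appendix A".

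Appendix A is the form itself, under the heading Caregiver Demographics. Its general instruction is "Please check the appropriate box or boxes". Item 3 asks for the relationship to the patient and offers eight answers. Three describe a partnership, the first being "Married or living as if married"; the other five are kinship or friendship ties.

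Section 7.3 (Analysis Plan) states: "We will use descriptive statistics to summarize the demographic and clinical characteristics of the caregivers enrolled in the study". It lists no variables.

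Three other places bear on where such data could come from:

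- Section 5.2.1 (Registration process) says of the requested HIPAA waiver: "This waiver is being requested to identify potential participants from a minimal chart review". The same section describes an eligibility checklist completed from the assessment in the research chart.
- Section 6.1 (Confidentiality) states: "Identifiers such as name will only be used during the initial data retrieval process". It does not say which records or variables are retrieved.
- Section 5.5.1 (Study Instrument Administration) places the exit interview as follows: "Upon completion of the intervention visits around day +90 (+/- 15 days) post-HCT".

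**The concern.** A reader who checks the text against the form finds that two promised variables do not line up. Nobody is asked about income. Relationship status and relationship to the patient are listed as two variables but share one item, so a son, sister or friend who ticks a single box leaves their own status unknown. Such caregivers are eligible, since section 4.1 admits relatives and friends. Nothing later in the study is planned to fill either gap.

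The clinical characteristics in section 7.3 raise a similar question, because the only baseline form is described as demographic and the only chart review described serves recruitment.

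What is at stake is the description of a very small sample whose opinions shape the intervention manual. If readers cannot tell who these caregivers were, they will find it harder to judge how far the feedback carries to others.

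**Working it through.** There is no stated figure to reproduce. The check sets the list in section 5.2 against the form.

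| Variable in section 5.2 | Appendix A |
|---|---|
| Age | item 1 (date of birth) |
| Gender | item 2 |
| Relationship to patient | item 3 |
| Relationship status | item 3, in part |
| Ethnicity | item 4 |
| Race | item 5 |
| Religion | item 6 |
| Education | item 7 |
| Household income | none |

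Items 8 to 10 (employment, years known, shared residence) are on the form but not in the list. The count is 7 matched + 1 partial + 1 absent = 9. The items run from 1 to 10 without a gap, so lost text does not explain the missing income item.

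**Item 3.** The eight options split into 3 partnership and 5 kinship or friend options. A caregiver who is the patient's partner gives both variables with one tick. For the others, the instruction allows more than one box. A child, parent or sibling who also ticks the married option can hardly mean marriage to the patient, so the second tick would reasonably be read as the caregiver's own status. A friend who ticks a second box stays ambiguous, and anyone who ticks one kinship or friend box gives no status.

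**How much could be missing.** Let p be the share of non-partner caregivers. The documents do not give p; assume 20% to 50%. If none of them ticks a second box, the share of listed values missing is (1 + p)/9:

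- p = 0.20: 1.20/9 = 13.3%
- p = 0.50: 1.50/9 = 16.7%

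Counting the three extra items as well (9 + 3 = 12 variables), it is (1 + p)/12, or 10.0% to 12.5%. If every non-partner gave a usable second tick, only income would be missing: 1/9 = 11.1%, or 1/12 = 8.3%. The figure therefore depends mainly on assumptions and on the choice of denominator. No decision rests on it.

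**Where the variables are used.** The only stated use is the descriptive sentence in section 7.3. The primary endpoint (section 7.1.1) is a finalized intervention based on qualitative findings. The sample size of 5 to 10 (section 7.2) is justified by saturation. The aspects to be refined under section 7.3 (content, structure and schedule, modality, further concerns) draw on caregivers' feedback. None of these uses income, relationship status or a clinical variable.

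**Clinical characteristics.** No variable is named. Even so, a caregiver-level clinical record is foreseen: the exclusion criterion in section 4.1 concerns psychiatric and cognitive conditions, and section 5.2.1 has the eligibility assessment documented in the research chart. The plan does not link that record to section 7.3, so it is a possible source rather than a specified one.

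**The case for a change.** The strongest case for acting is that the sponsor chose these variables, the correction is tiny, and the form is completed at consent or within 72 hours of enrolment (section 5.1, Study Research Subject Entry), so alignment is easiest before the first caregiver enters. No later collection is planned either. None of the 22 items of the exit interview guide asks for income or status, and the last is only an open question: "Is there anything else that you would like to add that we have not discussed". The sample description is also the only descriptive-statistics summary that section 7.3 specifies.

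Most of this stands as fact. The income item is missing, status is incomplete, and section 7.3 is vague on clinical variables. What does not stand is the step from these facts to a needed change in the plan. The exit guide covers acceptability and benefit, so its silence on demographics is expected. Staff are in contact with caregivers until about day +90, so a missing answer could be obtained with one question, although no section provides for it. With 5 to 10 people, most of the description (age, gender, race, ethnicity, religion, tie to the patient, education, employment, residence) is available without the two affected variables.

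The name, email and telephone fields on the form might also seem to conflict with identification by ID number in section 5.4. That section itself provides for a separate name-to-ID link, so there is no contradiction.

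**Conclusion.** The disagreement between text and form is genuine but clerical: of nine listed variables, one is absent and one is partly captured. The undefined clinical characteristics are a gap that an analyst fills by tabulating what was recorded and leaving out what was not. The effect is confined to one or two rows of a descriptive table for 5 to 10 caregivers. The endpoint, the sample size and the refinement of the intervention would be the same whichever way text and form were reconciled, so no change to the plan is called for.

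This rests on two conditions found in the documents: Phase 1 makes no comparison and adjusts for no baseline variable, and section 2.1 requires a separately approved amendment before the randomized Phase 2 begins. It does not depend on the assumed share of non-partner caregivers.

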### **5.3 Description of Intervention**

The multicomponent psychological intervention is described in detail in section 5.1. It entails eight individual sessions (30-45 minutes each) starting prior to admission for HCT and continuing until day + 70 after HCT, which will provide sufficient dose to promote effective coping and reduce caregiving burden. We will coordinate sessions with hospital and clinic visits or conduct them via phone to minimize participant burden and facilitate adherence. [name] (a behavioral psychologist and researcher) will deliver the intervention. [name] has extensive experience as a therapist on NIH-funded trials.

### **5.4 Data Collection**

We will audio-record all qualitative exit interviews and save them on HIPPA-compliant electronic storage. We will transcribe the interviews and we will save the text documents on HIPPA-compliant electronic storage for qualitative analysis. All additional data will be stored in locked cabinets at MGH as well as password-protected computer files, accessible only to trained study staff. Participants' data will be identified by an ID number only, and a link between names and ID numbers will be kept in a separate file under lock and key.

### **5.5 Description of Study Process**

#### **5.5.1 Study Instrument Administration**

After signing consent, we will schedule caregivers for their intervention visits with [name]. Upon completion of the intervention visits around day +90 (+/- 15 days) post-HCT, the trained research assistant or the principal investigator will conduct the qualitative exit interviews with study participants using a semi-structured interview guide (Appendix B). The interview will last approximately 30 minutes. Participants will be asked to be frank and will be reminded that there is no right or wrong answer to any question. Participants will also be reminded that they may refuse to answer any question that they choose. Drs. [name] (Principal investigator), and [name] (clinical psychologist and co-investigator) will be available to provide support and supervise the qualitative interview process.

#### **5.5.2 Intervention Administration**

Please see sections 5.1 and 5.3 as discussed previously regarding the intervention visits.

#### **5.5.3 Special Concerns**

We do not anticipate any complications with this study. If a participant expresses distress during the psychological intervention visits or exit interviews, they will be reassured by the psychologist and the research staff that they can stop the intervention and they need not to answer any of the interview questions which they find upsetting. They will also be reminded that study participation is voluntary. If participants remain distressed, both the Principal Investigator and the oncologist will be notified. Additionally, we will offer participants who remain distressed an opportunity to meet with either the principal investigator ([name]) or a clinical psychologist ([name], a co-investigator) to help address their distress.

**5.5.4 Compensation:** There will be no compensation for participating in this study.

## **5.6 Adverse Reactions and Their Management**

### **5.6.1 Reporting Adverse or Unanticipated Events**

We do not anticipate any harm with our study procedures. While some topics probed during the intervention are sensitive in nature, no adverse or unanticipated events occurred in previous studies of psychological interventions conducted by our research group. Additionally, our research team has extensive experience conducting psycho-behavioral interventions and qualitative interviews on sensitive topics without any adverse events. Should adverse or unanticipated events occur during the course of the study, a trained study staff member will report the events to the IRB as soon as they are discovered.

### **5.6.2 Anticipated Reactions**

If a participant expresses distress during the psychological intervention visits or exit interviews, they will be reassured by the psychologist and the research staff that they can stop the intervention and they need not to answer any of the interview questions which they find upsetting. They will also be reminded that study participation is voluntary. If participants remain distressed, both the Principal Investigator and the oncologist will be notified. Additionally, we will offer participants who remain distressed an opportunity to meet with either the principal investigator ([name]) or a clinical psychologist ([name], a co-investigator) to help address their distress.

### **5.6.3 Reaction Management**

Should caregivers experience distress during the intervention or the qualitative exit interview, Drs. [name] (oncologist) and [name] (clinical psychologist) will be available to address their acute needs. Should participants require further support, we will offer them an opportunity to meet with the outpatient social worker for additional follow-up.

